9.4 Statistical Methods

9.4.1 Statistical Outlier Determination

No statistical outlier analysis is planned.

9.4.2 Predetermined Covariates and Prognostic Factors

In Part C there will be a subanalysis performed for patients with baseline platelet level of $\leq 30 \text{ vs} > 30 \times 10\%$.

9.4.3 Hypothesis Testing

No formal hypothesis testing will be done.

9.5 TFL Layout

Report layout will be according to the PRA EDS – ICH E3 compliant – CSR Template. The layout of TFLs will be according to the PRA EDS standards.

No table shells will be provided. The TFLs will be provided in Adobe PDF format.

Format:

- Page size: A4
- Data in listings will be sorted by study part, cohort, site number (if applicable: each site on a new page), subject number and time point.
- Data in tables will be sorted by study part, treatment and time point.

- Column titles will be in title case letters.
- All tables and listings will be in landscape format.
- The treatment labels listed below will be used in the TFLs. Treatments will be sorted by investigational product (placebo then M254 then IVIg) then dose level (increasing mg/kg) then number of doses. These labels will be modified to account for the dose selected as part of dose escalation and the initiation of each part:

. . .

- Part A: ○ Placebo
- 3 mg/kg M254 HV (Healthy Volunteers)
- o 10 mg/kg M254 HV
- 30 mg/kg M254 HV
- o 60 mg/kg M254 HV
- o 120 mg/kg M254 HV
- 250 mg/kg M254 HV
- M254 HV total

Part B and C:

Data will be first presented by cohort and within cohort by treatment period according to following layout:

60 mg/kg M254		120 mg/kg M254		Total				
M254 period	IVIg period	Diff	M254 period	IVIg period	Diff	M254 period	IVIg period	Diff
XXX	XXX	XXX	XXX	XXX	XXX	XXX	XXX	XXX
XXX	XXX	XXX	XXX	XXX	XXX	ххх	XXX	ххх
The fell	مالة سمامم بمماشيته	الأسد ملمما	he used in Deut	D.				

The following cohort labels will be used in Part B:

- o 60 mg/kg M254
- o **120 mg/kg M254**
- o 250 mg/kg M254
- o 500 mg/kg M254
- o Total

The following cohort labels will be used in Part C:

- XXX mg/kg M254 (XXX will be replaced by the actual dose level)
- Total

Pooled Part B and C:

- XXX mg/kg M254 (XXX will be replaced by the actual dose level)
- o M254 total
- o 1000 mg/kg IVIg

Part D (planned treatment):

- XXX mg/kg M254, 3 doses (XXX will be replaced by the selected mg/kg dose level)
- XXX mg/kg M254, 4 doses (XXX will be replaced by the selected mg/kg dose level)
- For the safety tables: XXX mg/kg M254 md (pooled)

Treatments in Part D will also be presented by actual treatment – that is if the number of doses differs from planned a separate summary will be presented.

10.0 Analysis Sets

Analyses	Randomized Set	Safety Set	Pharmacokinetic Set	Full Analysis Set	Per Protocol Set
Disposition Summaries	\checkmark				
Safety Assessments		\checkmark			
Baseline Characteristics		\checkmark			
PK Concentrations			\checkmark		
PK Parameters			\checkmark		
PD Concentrations				\checkmark	\checkmark
PD Parameters				\checkmark	\checkmark

10.1 Safety Set

The safety set will consist of subjects who receive at least one dose of M254 or IVIg or placebo. This set will be used for the safety data summaries and baseline characteristic summaries.

10.2 Pharmacokinetic Set

The PK set will consist of all subjects who receive at least 1 dose of M254 or IVIg with at least 4 evaluable data points adequate to create an evaluable serum concentration profile. This set will be used for PK concentration and parameter summaries.

10.3 Full Analysis Set

The FAS (Full Analysis Set) will consist of all subjects included in the safety set for whom at least 1 post-infusion PD assessment was completed.

10.4 Per Protocol Set

The PP (Per Protocol) set is a subset of the FAS and will include participants who complete the study with all planned safety, PD, and PK assessments and no major protocol deviations impacting safety or PD assessments.

10.5 Randomized Set

The Randomized Population set will include all subjects who were randomized (subjects who have received a randomization number). This set will be used for the disposition summaries.

11.0 Subject Disposition

The number and percentage of subjects randomized, dosed, and members of each analysis set will be presented. The number and percentage of subjects who withdrew from the study prematurely and a breakdown of the corresponding reasons for withdrawal will also be presented.

12.0 Protocol Deviations and Violations

Protocol deviations/violations will be included in the CSR.

13.0 Demographic and Baseline Characteristics

13.1 Demographics

All demographic data as collected during the screening visits will be listed by subject. Site identification number will be included in this listing.

Subject demographics will be summarized descriptively for all subjects by part and treatment or in case of Part C by treatment sequence. The summary will include the subjects' age (in years), gender, race, ethnicity, weight (in kg), height (in cm), and BMI (in kg/m²). Demographics will be summarized for the safety and PP sets.

13.2 Medical History

Medical history will be listed. The medical history will be coded according to the latest version of the Medical Dictionary for Regulatory Activities. For Parts B,C and D, a separate listing of ITP history will be created, including date of diagnosis, platelet level at screening, information if splenectomy was performed and if patient has received IVIg therapy before.

13.3 Other Baseline Characteristics

Drug and alcohol screen results will be listed.

Serology results will be listed (hepatitis B surface antigen, Hepatitis C virus, and human immunodeficiency virus).

Pregnancy (β human chorionic gonadotropin [hCG]) results will be listed.

Non-compliance to inclusion or exclusion criteria (if any) will be listed.

14.0 Concomitant Medications

Medication and coding will be listed. There will be a separate listing of previous ITP medications for ITP patients in Parts B, C and D. The medications will be coded using the latest version of World Health Organization (WHO) Drug Dictionary Enhanced (DDE). Medications with an end date prior to the first dose of study drug will be considered prior medications and will be in a separate listing. If a partial date allows a medication to be considered concomitant, it will be categorized as such.

15.0 Treatment Compliance and Exposure

Study drug administration data will be listed, including date, start and end times of infusion, amount, volume, infusion completion / interruption details and comments.

16.0 Pharmacokinetic Analyses

16.1 Pharmacokinetic Variables

PK concentrations will be collected in serum and analyzed by PRA Bioanalytical Laboratory. The analysis described below will be performed at the end of the study.

16.1.1 Serum Variables

16.1.1.1 Concentrations

- Serum concentration of M254 (if receiving M254 in the current period)
- Total IgG serum levels and changes from baseline (if receiving IVIG in the current period)

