- m All systemic infusion reactions and associated AEs will be graded using Common Terminology Criteria for Adverse Events (CTCAE)
- Patients with ITP may be admitted to the unit the morning of Day 1so any procedure specified on Day -1 can occur on Day 1, but all results must be back before infusion begins. Likewise, any pre-infusion assessment specified on Day 1 can occur on Day -1 and does not need to be duplicated.
- Study staff should follow-up with the patient approximately 12 hours post-discharge for safety via phone call.
- p Discharge from study after final study period unless further follow-up of open AEs is deemed necessary by the Investigator.
- q IVIg infusion will occur on this day if patient's platelet count meets criteria, and then the Schedule of Activities should be followed starting at Day 1. For Period 2, Day 1, any assessments completed on the same date for Period 1 follow-up do not need to be duplicated.
- Blood sample for PK is required during the M254 treatment period only. It is NOT needed for the IVIg treatment period.
- ITP-BAT to be completed separately at Day 1 and 29 of each period (M254- and IVIg-treatment). Only 1 ITP-BAT assessment is needed if Day 29 of the first period is the same as Day 1 of the second period.
- t ECG and vital signs assessments required at the end of the infusion may be initiated 15 minutes prior to the end of infusion
- u These should be conducted as abbreviated physical exams
- PK sample is required prior to the start of infusion (on the day of the infusion).
- W Biomarker samples are collected at pre-infusion, Day 2, and Day 8; ADA samples are collected at pre-infusion and Day 29 follow-up. Please refer to the lab manual for specific instructions.

Compound: M254

Protocol: MOM-M254-001

Table 1-3. Part C Schedule of Activities (USA sites included)

(Schedule of Activities below is repeated when the patient receives their second infusion, which will be either M254 or IVIg)

Day	-28 to -2	-1 m	1 m	1	1	1	1	1	2	3 b	4 b	5 b	8±1 b	10 ±3 b	12 ±3 b	15 ±3 b	18 ±3 b	22 ±3 b	29 ±3 n
	Screening	Pre-infusion	Infusion		Post-infusion											Follow-up			
Procedure a Hour		0	0	0 (end of infusion)	0.25	0.5	2	4	0	0	0	0	0	0	0	0	0	0	0
Informed Consent	X																		
Demographics	X																		

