## 4.1.2 Part B (USA sites included)

Initiation of any cohort in Part B will only proceed on the recommendation of the SRC after safety data from Part A Cohort 4 at the 60-mg/kg dose level has been reviewed and confirmed by SRC.

Part B is a single-ascending-dose, fixed-sequence, open-label part to assess safety, tolerability, PK, and PD of M254 followed by 1000 mg/kg IVIg in approximately 4 cohorts of 2 ITP patients per cohort. Planned doses include 60, 120, 250, and 500 mg/kg. Up to 2 additional cohorts may be added based on findings in prior cohorts to better understand the safety of M254 and/or to better understand the efficacy to assist with dose selection for Part C. The maximum dose for Part B will not exceed 500 mg/kg. (The no-observed-adverse-event-level [NOAEL] of 1000 mg/kg was determined in the toxicology study in cynomolgus monkeys.) Additional patients to dosing cohorts may be added on the recommendation of the SRC.

Following screening to confirm eligibility to participate, patients will be dosed with M254. Please refer to Section 4.3.1 and Figure 1-3 for dosing details. There will be a 14-day safety monitoring period between enrollment of the first and second patients in the 500 mg/kg cohort.

Safety and platelet assessments will be conducted initially out to Day 28 post M254 administration. Patients will receive a fixed dose of IVIg at 1000 mg/kg on Day 29 if the patients' platelet count returns to  $\leq 15\%$  above baseline level. Patients whose platelets have not returned to  $\leq 15\%$  above baseline dosing level by Day 28 will have platelet determinations weekly until platelets return to  $\leq 15\%$  above baseline, up to 56 days postdose. If these conditions are not met by Day 57, IVIg will be administered, as long as the patients' platelets have returned to  $\leq 50 \times 10^9/L$ . If the platelets have not returned to  $\leq 15\%$  above baseline and are  $\geq 50 \times 10^9/L$ , the patient will complete Follow-Up assessments and be discharged from Part B. After dosing with IVIg, safety and the other assessments listed in the Schedule of Activities will be conducted for 28 days following IVIg administration.

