## **6.6** Dose-Cohort Study Escalation Rules

In this study, Parts A and B are dose-escalating; Parts C and D are not dose-escalating.

A dose escalation report (DER) will be provided by the Investigator to the Independent Ethics Committee (IEC) (where required) following completion of each dose level. The SRC will approve escalation to the next dose only if none of the stopping criteria have been reached, the safety and tolerability (and PD for Part B) out to Day 10 are acceptable, and there are no concerns regarding delayed significant AEs in earlier cohorts.

The minimum number of participants required to decide on dose escalation is 2 participants on active treatment (ie, a total of at least 3 subjects in Part A at all dose levels; and 2 patients in Part B); in Part B for dose levels precedented as tolerated with safety reviewed in Part A, only 1 subject is required for dose escalation though 2 will remain planned for the cohort.

Based on absence of significant toxicity in the Good Laboratory Practice (GLP) toxicity studies, escalation to the next higher dose will be up to approximately CCI. Based on emerging safety data (and PD data in Part B), lower or other intermediate dose(s) may be used, for instance when anticipated that after a planned dose escalation stopping criteria will be met. Pharmacokinetic data is not deemed necessary for dose escalation since IV dosing of this modified IgG has predictive exposures (100% bioavailability, volume of distribution [Vd] and clearance expected to be similar to endogenous IgG). There are no significant toxicity findings in the preclinical studies, and the maximum exposure in healthy volunteers is expected to remain well below exposures of the high dose (1000 mg/kg) used in GLP toxicity studies. In patients the maximum exposure is not expected to be above the high dose (1000 mg/kg) used in GLP toxicity studies.

Compound: M254 Protocol: MOM-M254-001

Protocol Date and Version:8 Global 28 April 2020

A more conventional 3+3 escalation design was considered but not employed in this study. A notable difference between the expectation of the design in the current study with 2 patients compared to a 3+3 design in literature is how the dose is used in the future. In the current study, [CC]

In a more conventional 3+3 design, a dose that triggers the 3+3 rule would be considered **tolerable**, and would be used for future study.

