Initiation of any cohort in Part B will only proceed on the recommendation of the SRC after safety data from Part A Cohort 4 at the 60 mg/kg dose level has been reviewed and confirmed by SRC. Part B is a single ascending dose, fixed-sequence, open-label part to assess safety, tolerability, PK, and PD of M254 followed by 1000 mg/kg IVIg in approximately 4 cohorts of 2 ITP patients per cohort. Planned doses include 60 mg/kg, 120 mg/kg, 250 mg/kg and 500 mg/kg. Up to 2 additional cohorts may be added based on findings in prior cohorts to better understand the safety of M254 and/or to better understand the efficacy to assist with dose selection for Part C. The maximum dose for Part B will not exceed 500 mg/kg (the NOAEL of 1000 mg/kg determined in the toxicology study in Cynomolgus monkeys). Additional patients to dosing cohorts may be added on the recommendation of the SRC. Patients will receive a fixed dose of IVIg at 1000 mg/kg on Day 29 if the patients' platelet count returns to \leq 15% above baseline level. Patients whose platelets have not returned to \leq 15% above baseline dosing level by Day 28 will have platelet determinations weekly until platelets return to \leq 15% above baseline, up to 56 days post-dose. If these conditions are not met by Day 57. IV lg will be administered, as long as the patients' platelets have returned to $< 50 \times 10^{9}$ /L. If the platelets have not returned to \leq 15% above baseline and are > 50 × 10⁹/L, the patient will complete Follow-Up assessments and be discharged from Part B. After dosing with IVIg, safety and the other assessments listed in the Schedule of Activities will be conducted for 28 days following IV lg administration.

Figure 3: Part B Schema

Note: Arrows represent dose escalation; Safety will be assessed prior to dose escalation.

IVIg = Intravenous immunoglobulin; NOAEL = no-observed-adverse-event-level.

- ^a Up to 2 additional cohorts may be added based on findings in prior cohorts. Additional patients may be added to cohorts, including prior dose level cohorts. Maximum dose will not exceed 500 mg/kg (a NOAEL of 1000 mg/kg determined in the toxicology study in cynomolgus monkeys).
- ^b All patients will receive a dose of IVIg (1000 mg/kg) at approximately Day 29.

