6.2 Randomization

A randomization schema will be developed for Part A and Part C and managed by the pharmacy at PRA in Netherlands for the study. Subjects will be randomized according to a randomization code generated by the Biostatistics Department of PRA.

Part A is randomized and double blind (sponsor unblind). Following screening to confirm eligibility to participate, subjects will be randomized to receive M254 or placebo. In Cohort 1, 5 subjects will be enrolled with 3:2 (active: placebo) randomization. In this cohort a sentinel group of 2 subjects (1 M254, 1 placebo) will be dosed and closely monitored for 48 hours before dosing the remainder of the cohort (2 M254, 1 placebo). In all other cohorts, subjects will be randomized 3:1 (active: placebo) with total of 4 subjects in each cohort.

Part C consists of 2 randomized, unblinded crossover cohorts. Each cohort consists of 10 patients with 2 arms in each cohort consisting of 5 patients in each arm, for an overall total of 20 patients in Part C. Following screening to confirm eligibility to participate, in each cohort subjects will be allocated to treatment sequence (M254-IVIg or IVIg-M254) in a 1:1 ratio (5 subjects will be allocated to sequence M254/IVIg and 5 subjects will be allocated to sequence IVIg/M254).

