9.2 Analysis Data Definitions

9.2.1 Baseline Definition

Unless otherwise stated, baseline for post-dose evaluations is defined as the last observation recorded before the first study drug administration. In case of Part B, C and D, baseline will be the last observation recorded before the first study drug administration in each period. The last observation can be an unscheduled / repeated measurement. If a pre-treatment observation is missing in a given period then the screening value may be used.

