16.1.1.2 Parameters

- PK Parameters for M254 as defined in Table 1: PK Parameters
- PK Parameters for total IgG (Immunoglubulin G) changes from baseline as defined in Table 1: PK Parameters

Table 1: PK Parameters

Parameter	Description	Part A Part B Part C F		Part D	SAS Programming	
		In all par	ts WNL in	Notes		
		• A • C to	bsolute v hanges fr otal IgG	alues for N om baseli	/1254 ne for	
C _{max}	Maximum serum concentration. Observed peak analyte concentration obtained directly from the experimental data without interpolation, expressed in concentration units	x	x	x	x	Cmax from WNL
t _{max}	Time to maximum serum concentration. First observed time to reach peak analyte concentration obtained directly from the experimental data without interpolation, expressed in time units.	x	x	x	x	Tmax from WNL
AUC _{0-last}	Area under the concentration-time curve (time 0 to time of last quantifiable concentration).	x	x	x		AUClast from WNL
AUC _{0-tau}	Area under the serum concentration-time curve over the dosing interval (time 0 to 15 days).				x	AUC0-tau from WNL where tau is equal to 15 days.
AUC _{0-inf}	Area under the serum concentration-time	x	x	x		AUCINF_obs from WNL

Parameter	Description	Part A	Part B	Part C	Part D	SAS Programming
		In all par • A • C te	rts WNL in Absolute v Changes fr otal IgG	puts are: alues for N om baseli	/1254 ne for	Notes
	curve (time 0 to infinity).					If AUC_%Extrap_obs >20% then parameter will be flagged, but not excluded from descriptive statistics
%AUC _{extra}	Percentage of estimated part for the calculation of AUC _{0-inf} . ((AUC _{0-inf} -AUC ₀₋ t)/AUC _{0-inf})*100%	x	x	x		AUC_%Extrap_obs from WNL
Kel	Terminal phase rate constant calculated by linear regression of the terminal log-linear portion of the concentration vs. time curve. Linear regression of at least three points is required to obtain a reliable k_{el} .	x	x	x		Lambda_z from WNL If Rsq adjusted ≤ .80 then parameter will be flagged, but not excluded from descriptive statistics.
t _{1/2}	Terminal phase half- life expressed in time units	x	x	x		HL_Lambda_z from WNL If AUC_%Extrap_obs >20% or Rsq ≤ .80 then parameter will be flagged, but not excluded from descriptive statistics.
Vz	Volume of distribution at terminal phase, calculated as CL/k _{el} .	x (M254 only)	x (M254 only)	x (M254 only)		Vz_obs from WNL
CL	Clearance, calculated as dose/AUC _{0-inf}	x (M254 only)	x (M254 only)	x (M254 only)		CL_obs from WNL

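### When IVIg is given second, the SAP's total-IgG half-life and AUC are taken from a baseline that can still hold decaying M254 IgG, so these descriptive IVIg values tend to be too low

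*SAP*

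**What the plan says.** SAP 16.1.1.1 names the analyte for an IVIg period as "Total IgG serum levels and changes from baseline (if receiving IVIG in the current period". SAP 16.1.1.2 then plans "PK Parameters for total IgG (Immunoglubulin G) changes from baseline as defined in Table 1: PK Parameters". For Parts B and C, Table 1 marks Cmax, tmax, AUC0-last, AUC0-inf, the extrapolated percentage, Kel and t1/2 for this input, and limits Vz, CL and MRT to M254.

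The baseline rule is in SAP 9.2.1: in Parts B, C and D "baseline will be the last observation recorded before the first study drug administration in each period". The Part B schedule of activities adds: "For Period 2, Day 1, any assessments completed on the same date for Period 1 follow-up do not need to be duplicated". The Part C schedule has the same footnote, so the Day 29 follow-up sample of Period 1 can serve as the Period 2 pre-dose sample.

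On sequence, protocol 4.1.2 describes Part B as a "fixed-sequence, open-label part to assess safety, tolerability, PK, and PD of M254 followed by 1000 mg/kg IVIg". In Part C, SAP 6.2 states for each of the two cohorts that "5 subjects will be allocated to sequence M254/IVIg and 5 subjects will be allocated to sequence IVIg/M254". For Part B, SAP 6.0 says: "Planned doses include 60 mg/kg, 120 mg/kg, 250 mg/kg and 500 mg/kg". Part C doses are left to be determined. The second infusion is given on Day 29 at the earliest and can come as late as about Day 57. What releases it is the platelet count; no rule refers to IgG.

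SAP 16.2.2 keeps negative total-IgG changes in the AUC, leaves the choice of terminal points to the pharmacokineticist (at least three), flags but keeps values with more than 20% extrapolation, and summarises by study part and treatment. It contains no correction for IgG remaining from the previous period.

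**The concern.** Subtracting a pre-dose value isolates the new dose only if the subtracted amount stays flat. Endogenous IgG may be roughly flat, but leftover M254 is not. It counts in total IgG, and protocol 6.6 has its "clearance expected to be similar to endogenous IgG", which implies slow elimination. As the leftover M254 falls during the IVIg period, the fixed baseline removes progressively too much. The error is largest at late times, and those times determine Kel, t1/2 and the extrapolated part of AUC0-inf.

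What is at stake is the descriptive picture of IVIg. Its half-life would look shorter than it is, most of all in patients who had received the most M254. A Part C mean would mix unaffected first-period profiles with affected second-period ones. SAP 9.5 also defines a pooled Part B and C layout with a single IVIg column. If that layout is used for these parameters and every planned patient receives IVIg, only 10 of 28 profiles (8 in Part B plus 20 in Part C) come from IVIg given first, or 10 of 40 if Part B grows to 20.

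**Working it through.** The plan states no half-life, residual or bias, so there is no figure of its own to reproduce.

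**Inputs from the documents.** IVIg dose 1000 mg/kg. Preceding M254 dose D1 = 60, 120, 250 or 500 mg/kg (Part B). Gap g between infusions of 28 days (Day 29) to 56 days (Day 57). Late sampling on nominal Days 8, 15, 22 and 29, that is t = 7, 14, 21 and 28 days after IVIg.

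**Assumptions.** Linear, mono-exponential decline; the same half-life h for M254 and IVIg, with h = 14, 21 or 28 days; constant endogenous IgG. Amounts are in mg/kg equivalents.

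**Formulas.**
- Residual at IVIg dosing: R = D1 × 2^(-g/h).
- True IVIg curve, with k = ln 2 / h: 1000e^(-kt).
- Curve analysed under the SAP: (1000 + R)e^(-kt) - R.
- Shortfall: R(1 - e^(-kt)), which is zero at dosing and grows with time.
- Apparent local rate constant: k(1000 + R)e^(-kt) / [(1000 + R)e^(-kt) - R]. This exceeds k whenever R > 0 and the analysed change is still positive, so the direction does not depend on the half-life chosen.

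**Worked case: D1 = 500, g = 28, h = 21.**
- R = 500 × 2^(-28/21) = 198.4, or 19.8% of the IVIg dose.
- True values at t = 14, 21, 28: 630.0, 500.0, 396.9. Analysed values: 556.5, 400.8, 277.2.
- Log-linear slope through the three equally spaced points: ln(556.5/277.2)/14 = 0.0498 per day, so t1/2 = 13.9 days instead of 21.0 (-34%).
- AUC0-28 = 1198.4 × (1 - 0.3969)/0.03301 - 28 × 198.4 = 16,343, against a true 18,273 (-10.6%).
- AUC0-inf = 16,343 + 277.2/0.0498, about 21,900, against 1000/0.03301, about 30,300 (about -28%).

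**28-day gap, range over h = 14 to 28 days.** AUC0-28 is AUC0-last when the last sample is Day 29. The AUC0-inf ranges cover both terminal windows.

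| M254 dose | R | t1/2, Days 15-29 | t1/2, Days 8-29 | AUC0-28 | AUC0-inf |
|---|---|---|---|---|---|
| 60 | 15 to 30 | -4.3 to -4.9% | -3.7 to -4.5% | -1.2 to -1.3% | -3.0 to -4.5% |
| 120 | 30 to 60 | -8.4 to -9.6% | -7.3 to -8.8% | -2.3 to -2.5% | -5.8 to -8.7% |
| 250 | 62.5 to 125 | -17.1 to -18.8% | -14.8 to -17.4% | -4.8 to -5.3% | -11.7 to -16.9% |
| 500 | 125 to 250 | -32.7 to -34.0% | -28.4 to -31.5% | -9.7 to -10.6% | -22.0 to -30.1% |

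**56-day gap after 500 mg/kg.** R = 31, 79 and 125 at h = 14, 21 and 28. The t1/2 bias is -8.8, -14.8 and -18.8% (Days 15-29), or -7.6, -13.3 and -17.4% (Days 8-29).

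**Sensitivity.** Let half the dose distribute with a 2-day half-life, with a terminal half-life of 21 days, a 28-day gap and a preceding dose of 500 mg/kg. This gives t1/2 -28%, AUC0-last -9.3% and AUC0-inf -22.8%. Over half-lives of 7 to 35 days and both gaps, no scenario reversed the sign.

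**Check of a remedy.** Subtracting R e^(-kt) instead of R returns the true values exactly in this model.

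**The case against.** The strongest reply is that little depends on these numbers. The PK endpoints concern M254, the primary efficacy analysis concerns platelets, no M254-versus-IVIg PK comparison is planned, and protocol 6.6 does not require PK data for escalation. IVIg clearance is not reported at all. This stands and makes the point minor. A reader might infer that the trial's comparison of M254 with IVIg is compromised; the documents do not support that.

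Three other strong readings also fail:
- **That every Part B patient is affected, from a Day 29 baseline.** Day 29 is only the earliest crossover, and some patients may leave Part B without IVIg. The Statistical Methods document bound with the SAP also reports that the Period 1 baseline was used when the Period 2 one was missing. In the model with h = 21 days and a 28-day gap, that leaves t1/2 correct but overstates AUC0-last by 2.4% (after 60 mg/kg) to 19.8% (after 500 mg/kg).
- **That the size needs no half-life.** At a 28-day gap the t1/2 bias is nearly constant over 14 to 28 days. At 56 days it roughly doubles over that range, and AUC0-inf varies at either gap.
- **That the SAP never separates sequences.** SAP 9.2.2 allows tables by sequence where applicable, Part B and C tables are laid out by cohort, and individual values and profiles are output. What remains is that section 16.2.2 does not require the split for these parameters.

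Two further replies stand. The largest biases follow 500 mg/kg, a Part B cohort of 2 planned patients. And the unaffected reference is imperfect: with 28 days of sampling, the extrapolated fraction 2^(-28/h) is 25, 40 and 50% at 14, 21 and 28 days, above the SAP's 20% flag each time.

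**Conclusion.** The concern holds in this limited form. For patients who receive IVIg second with a Period 2 baseline, the SAP's rules subtract a constant that can contain decaying M254 IgG, and IVIg t1/2, AUC0-inf and, to a lesser degree, AUC0-last are biased downward. The direction follows from those rules under linear kinetics and stable endogenous IgG. The size rests on an assumed common half-life, the preceding M254 dose, the gap and the terminal window. It runs from negligible for AUC after 60 mg/kg to roughly a third of the half-life after 500 mg/kg at the shortest gap. No Part C size can be stated because its M254 doses are open. The affected outputs are descriptive, so this is a low-priority correction, but a cheap one.

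**What to change.** In SAP 16.2.2 and in the pooled Part B and C layout of 9.5:
- present total-IgG parameters for IVIg by period, which in Part C means by sequence;
- base the pooled IVIg Kel, t1/2 and AUC0-inf on IVIg given in Period 1 of Part C (10 planned patients), keeping the flag for more than 20% extrapolation;
- show Period 2 values in their own columns, marked as affected by residual IgG, so that they are not lost;
- optionally, add a sensitivity analysis that subtracts a decaying rather than a constant residual, with the assumed half-life stated.

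Replacing the Period 2 baseline with the Period 1 value is not a substitute, since it moves the AUC error in the other direction.

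The cost is a short change of SAP wording and one extra split in the tables, with no new data. The downside is fewer IVIg profiles in the pooled summary, and the retained t1/2 and AUC0-inf will often still carry the extrapolation flag.
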